Subjects will not be permitted to receive supplemental buprenorphine during the RBP-6000 treatment period (Day 1 to EOS/ET Visit). Subjects who require supplemental buprenorphine pharmacotherapy during the RBP-6000 treatment period will be withdrawn from the study and referred for appropriate treatment. [Note: If subjects complete their EOS/ET Visit and a new treatment venue for them has not been identified, the Investigator may provide the subject further buprenorphine treatment or another appropriate treatment according to their own medical judgement.]

Subjects will return to the site for monthly injection visits every 28 days (-2 / +7 days) for a total of up to 6 injections. Subjects are not required to complete all 6 injections and may choose to “early terminate” (ET) the study at any time.

At each subsequent visit (Injection Visits 2 through 6) the following procedures and assessments will be performed: urine pregnancy test for all female subjects who are of childbearing potential before each injection; evaluation of previous injection site for potential reaction and evidence of attempts to remove the depot; collection of vital signs pre- and post-injection; RBP-6000 injection; urine drug screen (UDS); C-SSRS since last visit assessment, counseling (manual-

guided behavioral therapy); local injection site grading; subject self-assessment of injection site pain (Injection site Pain VAS); use of concomitant medications; and assessment for AEs.

Laboratory tests (hematology, chemistry and urinalysis) may be requested by the Investigator on an ad-hoc basis as necessary to further examine any AEs.

[figure not shown]
Alternative treatment options should be assessed at least two months before EOS at each visit, however it is recommended where possible to assess at every visit.

At the EOS/ET Visit, the following procedures and assessments will be performed: urine pregnancy test for all female subjects who are of childbearing potential; evaluation of previous injection site for potential reaction and evidence of attempts to remove the depot; vital sign measurements; UDS; C-SSRS “since last visit” assessment, counseling (manual-guided behavioral therapy); use of concomitant medications; assessment for AEs; brief physical exam; height and body weight measurement (to determine a subject’s BMI); hip and waist circumference (to determine a subject’s hip-to-waist ratio); and laboratory tests (hematology, chemistry, urinalysis).

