## **6.4 Vital Signs**

Evaluation of vital signs will be performed after the subject has been supine for  $\geq 3$  minutes and will include a measurement of systolic and diastolic blood pressure, pulse rate, pulse oximetry, respiratory rate, and oral temperature.

If clinically significant findings, as determined by the Investigator or medically qualified Sub-investigator, occur in any vital sign measurement, that measurement will be captured as an AE and repeated at medically appropriate intervals until the value returns to an acceptable range, a specific diagnosis is established, or the condition is otherwise explained.

Assessments will be recorded in the source documents and eCRF and will be performed at the time points detailed in the SOE ([Appendix 1](#)).

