12.1.9 Respiratory Depression Topic of Special Interest

A summary of TEAEs related to respiratory depression, as defined in Appendix 1, will be summarized by SOC and PT for the Safety Analysis Set.

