Post-injection delirium sedation syndrome	Cerebrovascular accident
Preictal state	Dizziness
Psychogenic pseudosyncope	Dizziness exertional
Mental status changes	Dizziness postural
Mental status changes postoperative	Procedural dizziness
Slow response to stimuli	Neurotoxicity
Unresponsive to stimuli	

CMQ LIST OF PREFERRED TERMS FOR RESPIRATORY DEPRESSION/RESPIRATORY FAILURE

Acute respiratory distress syndrome	Neonatal respiratory arrest
Acute respiratory failure	Neonatal respiratory depression
Apnoea	Neonatal respiratory distress syndrome
Apnoea neonatal	Neonatal respiratory failure
Infantile apnoea	Respiratory arrest
Apnoeic attack	Respiratory depression
Bradypnoea	Respiratory depth decreased

Breath sounds absent	Respiratory distress
Cardio-respiratory distress	Respiratory failure
Central-alveolar hypoventilation	Respiratory paralysis
Chronic respiratory failure	Respiratory rate decreased
Hypopnoea	Severe acute respiratory syndrome
Hypoventilation	Cardio-respiratory arrest
Hypoventilation neonatal	Cardio-respiratory arrest neonatal
Lung hypoinflation	Cardiopulmonary failure
Meconium aspiration syndrome	

CMQ LIST OF PREFERRED TERMS FOR ORTHOSTATIC HYPOTENSION

Orthostatic hypotension	Syncope
Vision blurred	Presyncope
Dizziness	Diastolic hypotension
Dizziness exertional	Hypotension
Dizziness postural	

CMQ LIST OF PREFERRED TERMS FOR WITHDRAWAL SYMPTOMS

Agitation	Malaise
Anxiety	Muscle spasms
Arthralgia	Muscle twitching
Bone pain	Myalgia
Chills	Mydriasis
Decreased appetite	Nausea
Depression	Piloerection
Diarrhoea	Pruritus
Dizziness	Psychomotor hyperactivity
Drug dependence	Pyrexia
Flushing	Respiratory rate increased
Heart rate increased	Restlessness
Hyperhidrosis	Rhinitis
Hypertension	Rhinorrhoea
Hypervigilance	Sneezing
Influenza like illness	Tachycardia

Insomnia	Tremor
Irritability	Vomiting
Lacrimal disorder	Yawning
Lacrimation increased	Drug withdrawal symptoms
Muscle strain	

CMQ LIST OF PREFERRED TERMS FOR ACUTE PANCREATITIS

Amylase abnormal	Oedematous pancreatitis
Amylase creatinine clearance ratio abnormal	Pancreatic abscess
Amylase increased	Pancreatic enzyme abnormality
Bilirubin conjugated abnormal	Pancreatic enzymes abnormal
Blood bilirubin increased	Pancreatic enzymes increased
Blood trypsin increased	Pancreatic haemorrhage
Cullen's sign	Pancreatic necrosis
Grey Turner's sign	Pancreatic phlegmon
Haemorrhagic necrotic pancreatitis	Pancreatic pseudocyst
Hereditary pancreatitis	Pancreatic pseudocyst drainage
Hyperamylasaemia	Pancreatitis

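### Low pulse oximetry findings recorded as AEs and coded to an oxygenation term fall outside the respiratory-depression topic table, because the SAP's respiratory term list contains no such term

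*SAP*

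**What the plan says.** SAP 12.1.9 defines the topic table entirely by reference to a term list: "A summary of TEAEs related to respiratory depression, as defined in Appendix 1, will be summarized by SOC and PT for the Safety Analysis Set". The list is in SAP Appendix 1 under "CMQ LIST OF PREFERRED TERMS FOR RESPIRATORY DEPRESSION/RESPIRATORY FAILURE", and the output is Table 14.3.1.17. One entry is a measurement term for a vital sign: "Respiratory rate decreased".

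Protocol 6.4 defines vital signs as "systolic and diastolic blood pressure, pulse rate, pulse oximetry, respiratory rate, and oral temperature". Section 3.1 requires "collection of vital signs pre- and post-injection" at Injection Visits 2 to 6. The Schedule of Events adds a post-injection set on Day 1 and a set at EOS/ET.

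Protocol 6.4 also states that if findings the investigator considers clinically significant "occur in any vital sign measurement, that measurement will be captured as an AE". Section 6.9.9 sets the same limit: changes in vital signs are reportable only when judged clinically significant.

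**The concern.** Respiratory depression is one of the risks the sponsor chose to report as a topic of special interest, and Table 14.3.1.17 is where a reader will look for it. The study takes two respiratory measurements at each injection visit: respiratory rate and pulse oximetry. The term list picks up an abnormality in the first but not in the second. The protocol tells sites to record a significant measurement as an AE, so a low reading may well be reported, and then coded, as a measurement finding and not as a diagnosis. In that case the topic table does not count it. Few events are likely, so one or two omissions could decide whether the table shows zero.

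**Working it through.** The plan states no figure for this point, so there is none to reproduce. The check compares the term list with what the study measures.

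**Step 1: count the list.** The respiratory list in SAP Appendix 1 has 31 distinct terms.
- Neonatal or infant terms: 9 (four neonatal respiratory terms, *Apnoea neonatal*, *Infantile apnoea*, *Hypoventilation neonatal*, *Cardio-respiratory arrest neonatal*, *Meconium aspiration syndrome*).
- Remaining terms that could apply to adults: 31 − 9 = 22. They include *Respiratory depression*, *Hypoventilation*, *Hypopnoea*, *Bradypnoea*, *Respiratory distress* and *Respiratory failure*.
- Terms naming oxygen, saturation, hypoxia or cyanosis: 0.

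**Step 2: compare with the SAP's other lists.** For each vital sign in Protocol 6.4, look for a matching abnormality in any Appendix 1 topic list.

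| Vital sign | Matching terms | List |
|---|---|---|
| Blood pressure | *Hypotension*; *Hypertension* | Orthostatic hypotension; withdrawal |
| Pulse rate | *Heart rate increased* | Withdrawal |
| Respiratory rate | *Respiratory rate decreased*; *Respiratory rate increased* | Respiratory; withdrawal |
| Oral temperature | *Pyrexia* | Withdrawal |
| Pulse oximetry | none | none |

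The hepatic and pancreatitis lists follow the same practice for laboratory values, with raised ALT, amylase and lipase. Pulse oximetry is the one vital sign without a matching term, and the SAP gives no reason.

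**Step 3: follow one event through the plan.** A low reading is judged clinically significant and recorded as an AE (Protocol 6.4).
- Coded to a listed diagnosis such as *Hypoventilation*: it enters Table 14.3.1.17.
- Coded to an oxygenation term: it matches 0 of 31 terms and does not enter.

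**Step 4: see where the second event does appear.** If treatment-emergent, it is in the TEAE summary by SOC and PT (SAP 12.1.1, Table 14.3.1.2). It is also in the AE listing (Listing 16.2.15). The readings are in the vital-sign summary and listing (SAP 12.3, Table 14.3.5.8, Listing 16.2.34).

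**Step 5: size.** The documents give no rate of desaturation AEs. For illustration only, assume a subject-level risk p of such an AE in 300 subjects. The expected number is 300p, and the chance of at least one is 1 − (1 − p)^300.

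| Assumed p | Expected subjects | Chance of at least one |
|---|---|---|
| 0.1% | 0.3 | 26% |
| 0.33% | 1.0 | 63% |
| 1% | 3 | 95% |
| 2% | 6 | 99.8% |

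These are upper bounds on what the topic table could miss, because some of these events would be coded to a listed diagnosis.

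**The case against.** The strongest reply is that nothing is lost. Every TEAE is tabulated by preferred term, every AE is listed, and pulse oximetry is summarised by visit and time point with change from baseline and pre- to post-injection change. The study has a single group and is descriptive, and no hypothesis or stopping rule depends on the topic count. How widely to draw a customised query is partly a matter of judgement, and the reason for this list's scope cannot be seen from the documents.

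Most of that stands, and it limits the point to one topic table. It does not remove the point. The vital-sign summary is descriptive and has no count of subjects with low readings, so it does not replace the topic table. The SAP's own lists include measurement terms for the other vital signs, which makes the omission look unintended.

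A reader might infer more than the documents support:
- *That every abnormal reading must become an AE.* Protocol 6.4 and 6.9.9 limit this to findings the investigator judges clinically significant.
- *That desaturation can never reach the table.* An event reported and coded as a listed diagnosis does. Protocol 6.4 provides for repeat measurement until, among other end points, a diagnosis is established.
- *That the number of readings measures the problem.* A completer has up to 1 + (5 × 2) + 1 = 12 scheduled on-treatment readings, or 12 × 300 = 3,600 if all 300 complete. That counts opportunities, not events, and subjects need not take all six injections.
- *That the nine neonatal or infant terms distort the table.* The SAP's age categories start at 18, so these terms should contribute no subjects and removing them changes no count.
- *That blood-gas terms should be added as well.* The protocol's laboratory list includes no blood-gas test, so they do not follow from pulse oximetry.

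**Conclusion.** The point holds in a limited form. Clinically significant low pulse oximetry findings that are recorded as AEs and coded to an oxygenation term are not captured in Table 14.3.1.17. The list has a term for low respiratory rate and none for low oxygen saturation or hypoxia. The effect is incomplete grouping in one special-interest table, with no loss of data from the report. The number of subjects affected is unknown and probably small.

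The conclusion assumes that at least some low readings are reported as measurement findings and not as diagnoses, and that such reports code to preferred terms outside the 31. The second assumption needs the MedDRA 19.0 dictionary to confirm. The correction is worth making because it is cheap and concerns a topic the sponsor singled out.

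**What to change.** Before database lock, add to the respiratory list in SAP Appendix 1 the MedDRA 19.0 preferred terms to which low pulse oximetry findings code. Candidates are oxygen saturation decreased and hypoxia, to be confirmed in the dictionary. Produce Table 14.3.1.17 on the extended list. If lock has passed, present the extended table as an unplanned analysis identified as such in the clinical study report, which Protocol 9.1 allows.

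The cost is an appendix edit and one table. The downside is that some non-specific hypoxia, for example with pneumonia, may enter the topic count. Those events remain identifiable because the table is by preferred term. Removing the neonatal terms and adding blood-gas terms are not needed.

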12.1.11 Orthostatic Hypotension Topic of Special Interest

A summary of TEAEs related to orthostatic hypotension, as defined in [Appendix 1](#), will be summarized by SOC and PT for the Safety Analysis Set.

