12.3 VITAL SIGNS

Measurements of vital signs (supine blood pressure systolic, supine blood pressure diastolic, pulse rate, oral temperature, respiratory rate, pulse oximetry, weight, height, BMI, hip circumference, waist circumference and waist-to-hip ratio) will be summarized using descriptive statistics at each scheduled visit and time point including change from baseline, percentage change from baseline and pre- and post- injection change if available.

Listings/tables of all vital sign assessments will be provided for the following groups:

- Supine blood pressure systolic, Supine blood pressure diastolic, Pulse rate, Oral temperature, and Respiratory rate, Pulse Oximetry;
- Body weight, BMI, Hip Circumference, Waist Circumference and Waist-to-hip ratio.

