Injection site dermatitis	Injection site movement impairment
Injection site erosion	Injection site lymphadenopathy
Injection site erythema	Injection site nodule
Injection site extravasation	Embolia cutis medicamentosa

Injection site fibrosis	Injection site scar
Injection site granuloma	Injection site discharge
Injection site haematoma	Injection site pallor
Injection site haemorrhage	Injection site papule
Injection site hypersensitivity	Injection site injury
Injection site hypertrophy	Injection site scab
Injection site induration	Injection site eczema
Injection site inflammation	Injection site streaking
Injection site irritation	Injection site dryness
Injection site mass	Injection site laceration
Injection site necrosis	Injection site macule
Injection site nerve damage	Injection site vasculitis
Injection site oedema	Injection site exfoliation
Injection site pain	Injection site dysaesthesia
Injection site paraesthesia	Injection site plaque
Injection site phlebitis	Injection site hyperaesthesia
Injection site pruritus	Injection site hypoesthesia
Injection site rash	Injection site hypertrichosis
Injection site reaction	
Injection site thrombosis	

CMQ LIST OF PREFERRED TERMS FOR CNS DEPRESSION

Mental fatigue	Hyporesponsive to stimuli
Microsleep	Benign familial neonatal convulsions
Narcolepsy	Febrile convulsion
Coma	Drug withdrawal convulsions
Impaired driving ability	Convulsion neonatal
Impaired ability to use machinery	Convulsions local
Accident	Tonic convulsion
Road traffic accident	Convulsion in childhood
Vision blurred	Clonic convulsion
Vertigo CNS origin	Acute encephalitis with refractory, repetitive partial seizures
Incoherent	Generalised tonic-clonic seizure
Disturbance in attention	Complex partial seizures

Judgement impaired	Psychomotor seizures
Mental impairment	Simple partial seizures
Borderline mental impairment	Autonomic seizure
Cognitive disorder	Atonic seizures
Altered state of consciousness	Seizure
Depressed level of consciousness	Partial seizures with secondary generalisation
Lethargy	Alcoholic seizure
Loss of consciousness	Partial seizures
Sedation	Seizure like phenomena
Somnolence	Seizure cluster
Somnolence neonatal	Change in seizure presentation
Stupor	Migraine-triggered seizure
Syncope	Psychogenic seizure
Postictal state	Seizure anoxic
Consciousness fluctuating	Post stroke seizure
Neonatal oversedation	Accidental death
Hypoglycaemic unconsciousness	Accidental overdose
Hyperglycaemic unconsciousness	Accidental exposure to product

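### The orthostatic-hypotension term list has no blood-pressure measurement term, so an adverse event coded as a fall in measured pressure would be left out of the topic table

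*SAP*

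**What the plan says.** SAP 12.1.11 plans "A summary of TEAEs related to orthostatic hypotension", by system organ class and preferred term, with the topic defined by Appendix 1. The list there, headed "CMQ LIST OF PREFERRED TERMS FOR ORTHOSTATIC HYPOTENSION", has nine terms: *Orthostatic hypotension*, *Hypotension*, *Diastolic hypotension*, *Syncope*, *Presyncope*, *Vision blurred*, *Dizziness*, *Dizziness exertional* and *Dizziness postural*. The output is Table 14.3.1.19, whose title describes the events as potentially pertaining to orthostatic hypotension.

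Protocol 6.4 says that if a vital sign is clinically significant, "that measurement will be captured as an AE and repeated at medically appropriate intervals". Protocol 6.9.9 likewise makes clinically significant vital-sign changes reportable as AEs. Vital signs are taken supine, and SAP 12.3 accordingly summarises "supine blood pressure systolic, supine blood pressure diastolic" with descriptive statistics and changes.

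**The concern.** The protocol invites AEs that are recorded as a measurement. If such an AE is coded to a preferred term for decreased blood pressure, no term on the list will pick it up, and Table 14.3.1.19 will omit it. The row-by-row display cannot reveal the gap, because an event whose term is not on the list has no row.

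What is at stake is the completeness of one safety-topic count. It matters somewhat more here because no scheduled reading is taken standing, so the study's own measurements cannot show an orthostatic fall, and the topic rests on AE terms.

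**Working it through.** The documents give no event rate or target figure for this topic. The check is therefore a comparison of lists plus some simple counts.

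**1. Sorting the nine terms.** Three name low pressure: *Orthostatic hypotension*, *Hypotension* and "Diastolic hypotension". Six are symptoms: 9 − 3 = 6. Terms worded as a blood-pressure measurement: 0 of 9.

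**2. What other Appendix 1 lists do.**

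| List | Condition term | Measurement term |
|---|---|---|
| Respiratory depression | *Bradypnoea* | *Respiratory rate decreased* |
| Withdrawal | *Tachycardia* | *Heart rate increased* |
| Acute pancreatitis | *Hyperamylasaemia* | *Amylase increased* |
| Acute pancreatitis | *Hyperlipasaemia* | *Lipase increased* |
| Hepatic | *Hyperammonaemia* | *Ammonia increased* |
| Withdrawal | *Hypertension* | none |
| Orthostatic hypotension | *Hypotension* and two related terms | none |

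The SAP thus treats the two wordings as separate preferred terms and usually lists both. The practice is general but not universal: *Hypertension* in the withdrawal list also stands without a blood-pressure measurement term.

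**3. How such an AE could arise.** Footnotes 4 and 5 of the schedule (protocol Appendix 1) give one post-injection set of vital signs on Day 1 and a set before and after each of Injections 2 to 6. The schedule adds one set at the EOS/ET visit. For a subject who completes, that is 1 + (5 × 2) + 1 = 12 scheduled sets after the first dose. Each is an occasion on which protocol 6.4 could produce an AE recorded as a measurement.

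**4. Where that AE would appear.** It would be in the all-TEAE table by system organ class and preferred term (Table 14.3.1.2) and in the AE listing (Listing 16.2.15). The reading itself would be in Listing 16.2.34 and, if from a scheduled visit, in Table 14.3.5.8. It would not be in Table 14.3.1.19. SAP 12.3 sets no low-pressure threshold and plans no count of subjects below one, so the vital-sign tables do not supply the missing count.

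**5. Size per subject.** At the planned enrolment of about 300, a subject whose only relevant event is coded this way lowers the topic percentage by 1/300 = 0.33 percentage points. A subject who also has a listed term is still counted in the topic total, but the measurement event has no row.

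**6. Overlap with other topics, relevant to presentation only.** The list headed "CMQ LIST OF PREFERRED TERMS FOR CNS DEPRESSION" has 73 terms and the withdrawal list 41. The orthostatic and CNS lists share *Dizziness*, *Dizziness exertional*, "Dizziness postural", *Syncope* and "Vision blurred": 5/9 = 56% of the orthostatic list. *Dizziness* is in all three lists. To show how far it could drive the total, assume dizziness in 1% to 5% of 300 subjects (3 to 15), a hypotension term in 0.2% to 1% (0.6 to 3), no subject with both, and no other listed term. The dizziness share then runs from 0.01/(0.01 + 0.01) = 50% to 0.05/(0.05 + 0.002) = 96%. These rates are assumptions; the documents give none.

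**The case against.** The strongest reply is that little is lost. An AE coded to any of the three hypotension terms is captured. Protocol 6.4 follows an abnormal reading until, among other end points, a diagnosis is established, so a hypotension term may be the one finally coded. A measurement-coded event stays visible in the all-TEAE table and the listing. The study has a single group and descriptive summaries, so no inference turns on this table. All of this stands and limits the size of the point. None of it puts the omitted event into the topic count.

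A second reply is that a fall seen in a supine reading is not shown to be orthostatic, so the added terms would widen the topic. That is true, but plain *Hypotension* and *Diastolic hypotension* already admit such events, so the additions stay within the scope the SAP has chosen.

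A reader might go further in three ways that the documents do not support:

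- **That low-pressure AEs in general are missed.** Only those coded to a measurement term are.
- **That dizziness is reported as orthostatic hypotension.** The table title says only that events potentially pertain to the topic, and *Dizziness* has its own row.
- **That the overlap makes the orthostatic, CNS-depression and withdrawal totals unreadable.** Nothing in the SAP says the lists are mutually exclusive, and other lists overlap too: *Hyperbilirubinaemia* is in both the hepatic and the pancreatitis lists. *Dizziness* is 1 of 73 CNS terms and 1 of 41 withdrawal terms. Nor are all five shared terms non-specific, since *Dizziness postural* names position.

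**Conclusion.** The point holds in a narrow form. The orthostatic-hypotension list lacks a measurement-type blood-pressure term, most comparable entries in Appendix 1 have one, and the protocol provides a route by which AEs of that type can arise. A TEAE coded that way would be left out of Table 14.3.1.19 but not out of the report.

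The number of such events cannot be determined from the documents; it could be zero. The conclusion rests on two assumptions: that MedDRA 19.0 has separate terms for decreased blood pressure, as the paired lists suggest but the documents do not show, and that some AEs would be coded to them. The consequence is a possible undercount in one descriptive table, which is worth correcting because the correction is so cheap. The shared terms are a matter of presentation and not an error.

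**What to change.** Add to the orthostatic-hypotension list in SAP Appendix 1 the measurement terms for decreased blood pressure, as they are named in MedDRA version 19.0, the version SAP 12.1.1 states. The list is a customised query, so the sponsor can extend it. The cost is a few added terms, with no new data and no protocol change. The downside is small: some low-pressure events that were not orthostatic will enter the topic, as already happens with *Hypotension*.

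Two optional changes would help the reader:

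- Give a subject subtotal in Table 14.3.1.19 for the terms that name low pressure, including the added ones, so that the total is not read without knowing how much of it is dizziness.
- Align the wording of SAP 12.1.11, which calls the events related to orthostatic hypotension, with the more cautious table title.
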